10. DATA AND SAFETY MONITORING PLAN

10.1. Adverse event reporting

Because the proposed research is considered no more than minimal risk, adverse events (AEs) related to the proposed strategies are not anticipated. The intervention in this study is focused on improving standard-of-care treatment of diabetes or hypertension delivered by the MOH health workers in MOH facilities. Therefore, it will be the responsibility of the MOH staff to provide care for patient participants who experience an adverse event (e.g., hypotension, hypoglycemia, or other adverse drug effects as noted in 11.3) to manage these patients according to MOH protocols. In our reporting role, the study team will review from MOH records

all serious AEs, unanticipated problems, and other reportable information or occurrence (ORIO) using an event form and reported using to the University of Michigan IRB using the standard timetable and grading scale, consistent with federal guidelines.⁷⁰

10.2. Monitoring the study

The study team will conduct monthly scheduled assessments of study recruitment, data integrity and quality, adverse events, withdrawals, and compliance with protocol. Research staff and MOH staff will be instructed to report in person or by telephone all complaints, protocol deviations, or unanticipated problems to the study coordinators. The study coordinator will be charged with gathering necessary information from this initial report and contacting the PI at the time of the event. No interim analyses are planned. The trial will not employ stopping rules or a Data Safety Monitoring Board because the study carries no more than minimal risk to participants. If there is available funding and the study investigators and Technical Advisory Committee think there would be potential benefit in extending the pilot trial, then an extension to may be considered (e.g., from 6 months to 12 months in duration).

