5.3. Participant eligibility criteria

5.3.1. *Patient participants*

Inclusion criteria: All non-pregnant adults aged ≥ 18 years with diagnoses of type 2 diabetes, hypertension, or both conditions who present for routine care at participating MOH primary health facilities between over a 6-month period will be included (“patient participants”).

Both previously diagnosed and newly diagnosed patients will be eligible. Previously diagnosed patients will be identified by MOH primary care clinicians who take medical histories as part of routine care. Newly diagnosed patients will be identified by MOH primary care clinicians who apply hypertension and diabetes diagnostic criteria from national guidelines.^{27,28}

- Diabetes diagnostic criteria for newly diagnosed patients: fasting glucose ≥ 126 mg/dl, two-hour post-prandial glucose ≥ 200 mg/dl, HbA1c $\geq 6.5\%$.
- Hypertension diagnostic criteria for newly diagnosed patients: include systolic blood pressure ≥ 130 mmHg or diastolic blood pressure ≥ 80 mmHg. A new hypertension diagnosis must be based on the average of at least two measurements performed on two separate occasions.

Exclusion criteria: Participants with confirmed or suspected type 1 diabetes or who are pregnant will be excluded, as these patients are not managed at MOH health centers or health posts. Participants with a prior history of cardiovascular disease will not be excluded.

[figure not shown]
5.3.2. *Other participants*

All MOH staff (physicians, nurses, auxiliary nurses) and stakeholders on the Technical Advisory Committee will be eligible for participation in the implementation assessment of the pilot (“MOH participants”). Details on the Technical Advisory Committee members are provided in 7.3.5.

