6. OUTCOMES

6.1. Primary outcomes

Primary outcomes will be feasibility and acceptability as defined in the Implementation Outcomes Framework (**Table 2**).³⁸ These outcomes will be assessed using quantitative data, qualitative data, and mixed methods (integrated qualitative and quantitative data). Given the study team's prior experience with HEARTS-aligned projects, the focus of the feasibility and acceptability assessments will be on integrating diabetes into the HEARTS model.

Feasibility is the extent to which a new intervention can be successfully carried out in an organization.³⁸ Among MOH participants, feasibility will be assessed through the four-item Feasibility of Intervention Measure (FIM) questionnaire³⁹ and semi-structured interviews. Among patient participants, feasibility will be assessed using enrollment data.

Acceptability is the stakeholders' perception that a new intervention is agreeable or satisfactory.³⁸ Among MOH participants, acceptability will be assessed using the Acceptability of Intervention Measure (AIM) questionnaire³⁹ and semi-structured interviews. Among patient participants, acceptability will be assessed using follow-up visit data and semi-structured interviews.

Table 2: Measures of feasibility and acceptability and their benchmarks

Measure	Minimum benchmark
Feasibility	
Feasibility questionnaire (FIM) among MOH participants	Median $\geq 3.5^a$
Reasons for perceptions of feasibility/infeasibility	N/A
Number of patient participants with diabetes enrolled per health district ^b	25
Number of patient participants with hypertension enrolled per health district ^b	25
Acceptability	
Acceptability questionnaire (AIM) among MOH participants	Median $\geq 3.5^a$

Table 2: Measures of feasibility and acceptability and their benchmarks

Measure	Minimum benchmark
Proportion of patient participants with subsequent follow-up visit within 3 months (among those enrolled with ≥ 3 months remaining in pilot)	75%
Reasons for perceptions of acceptability/infeasibility among patient and MOH participants	N/A
Reasons for dropouts among patient participants	N/A

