Primary outcomes in this pilot study are feasibility and acceptability as defined in the Implementation Outcomes Framework. ^a The FIM and AIM scales range from 1 to 5 with higher values implying greater feasibility or acceptability, respectively; scores are averaged within each participant. ^b Enrollment is defined by a patient having at least one clinic visit entered in the DHIS2 or equivalent longitudinal medical record system; a given patient may have both diabetes and hypertension and thus count toward each benchmark. Abbreviations: AIM: Acceptability of Intervention Measure; FIM: Feasibility of Intervention Measure; MOH: Ministry of Health.	

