7.2. Recruitment and sampling

[figure not shown]
This project is embedded in MOH-led standard routine primary care services. All new or existing patients with diabetes or hypertension receiving care at the participating MOH primary care facilities will be enrolled in the DHIS2 system. Recruitment activities will be carried out that align with the routine outreach activities of each MOH health facility; these activities may include

meetings with local leaders, public posters, and brief announcements on social media platforms or the radio.

A subset of patient participants (n=10, of whom n=5 from each health district) will be recruited for questionnaire assessments and interviews. These patient participants will be purposively selected among individuals who had enrolled in the first two months of the study and had high versus low numbers of patient visits (i.e., explanatory sequential mixed methods sampling). Study fieldworkers who are not MOH employees will make an initial contact via home visit, phone calls, or encounters at MOH health facilities. Participants who express interest in this part of the study will then receive a visit by study fieldworkers to complete informed consent and interview assessments. This visit will occur in the patient's home or another convenient private location, depending on the patient's preference.

All MOH participants and members of the Technical Advisory Committee will be asked to complete a structured questionnaire. The study team will use lists of personnel participating in trainings and contacts at each health district to identify MOH participants. Members of the Technical Advisory Committee will be recruited using INCAPs local contacts and connections from prior projects with the MOH. Subsequently, a subsample of approximately 20 MOH participants will be purposively selected for semi-structured interviews based on high versus low perceptions of intervention feasibility (i.e., explanatory sequential mixed methods sampling). Mixed-methods procedural diagrams are shown in **Figure 4**.

Figure 4: Mixed-methods procedural diagram

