8. SAMPLE SIZE CONSIDERATIONS

Primary health facilities. The sample of health facilities will include nine health posts and 2 health centers for a total 11 primary health facilities. No formal sample size calculation was performed.^{62,63} This sample of health facilities and population size of pilot health districts is consistent with recommendations in the HEARTS Implementation Guide.²²

Table 4: Semi-structured interview sample

Actor	Number ^a
Participants with diabetes	10
MOH physicians or physicians-in-training	4
MOH professional nurses	4
MOH auxiliary nurses	10
MOH administrators	2
Total	30

^aThe interview sample will be stratified by sex (target of 50% men and women by actor) and by health district (target of 50% from each health district).

Patient participants. The target sample of patient participants will be approximately 100 individuals, or 50 participants per health district. Based on the study team's prior experience, the

anticipated breakdown is n=45 patients with hypertension only, n=45 with diabetes only, and n=10 patients with both hypertension and diabetes. However, it is possible that the improved clinical services may attract a greater number of patients to MOH care than anticipated for the pilot. Of these, a subsample of 10 participants with low versus high retention levels (defined by number of clinical visits within the study time period) will be selected for semi-structured interviews at the close of the study. To improve understanding of how diabetes can be integrated into the HEARTS hypertension primary care model, we will purposely sample patient participants with diabetes.

MOH participants. The anticipated sample of MOH participants working to implement HEARTS will be approximately 50 participants. Of these, a subsample of 20 will be selected for semi-structured interviews at the close of the study using the breakdown shown in **Table 4**.

Including patient and MOH participants, a total of 30 semi-structured interviews are planned to achieve thematic saturation.^{64,65} The interview sample will be sex-stratified with a target of 50% men and women by actor. Interviews will be analyzed as they are conducted, and more may be added if saturation is not achieved.⁶⁶

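### If the pilot is extended beyond 6 months, does the enrolment benchmark of 25 per condition per district become too easy to meet?

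*Combined protocol and SAP*

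**What the plan says.** Section 10.2 allows a longer pilot if money is available and both the investigators and the Technical Advisory Committee see potential benefit: "an extension to may be considered (e.g., from 6 months to 12 months in duration"). It does not mention the benchmarks. The same section provides for regular recruitment review: "The study team will conduct monthly scheduled assessments of study recruitment".

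Table 2 (section 6.1) lists "Number of patient participants with diabetes enrolled per health district" with a minimum of 25, and a matching row for hypertension. Footnote b adds: "Enrollment is defined by a patient having at least one clinic visit entered in the DHIS2 or equivalent longitudinal medical record system". Neither the rows nor the footnote carries a cut-off date. The follow-up row has a 75% minimum and restricts its denominator to patients "among those enrolled with ≥ 3 months remaining in pilot".

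The time frame is set elsewhere. Section 5.1 describes a pilot of 6 months. Section 5.3.1 says that eligible adults "who present for routine care at participating MOH primary health facilities between over a 6-month period will be included", and gives these people the label patient participants. The wording there is garbled, but the length of the period is clear. Section 7.2 makes enrolment part of routine care: "All new or existing patients with diabetes or hypertension receiving care at the participating MOH primary care facilities will be enrolled". Section 8 expects about 100 patients, 50 per district: "anticipated breakdown is n=45 patients with hypertension only, n=45 with diabetes only, and n=10 patients with both hypertension and diabetes".

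**The concern.** A cumulative count with no date attached gets easier to reach the longer one waits. Section 7.2 enrols everyone in care, so the tally keeps rising for as long as enrolment is open. The margin is thin: the plan expects about 27.5 per condition per district against a minimum of 25, so a miss at 6 months is plausible even if recruitment goes as expected. The people who share the extension decision see recruitment figures as the trial runs. A district that missed 25 at month 6 could then be reported as having met it at month 12, and a Ministry of Health reader planning scale-up might not know which period was used.

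The follow-up row seems to have the same weakness, because its denominator refers to time remaining in the pilot and so moves with the end date.

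**Working it through.** **1. The plan's own figures.** From section 8: 45 + 45 + 10 = 100 in total, and 100/2 = 50 per district, as stated. Footnote b lets a patient with both conditions count toward each benchmark, so each condition has 45 + 10 = 55. Split equally between districts (an assumption; section 8 gives no condition mix by district) that is 55/2 = 27.5, or 27.5/6 = 4.58 per month.

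**2. Required rate.** 25/6 = 4.17 per month and 25/12 = 2.08 per month. The 12-month requirement is half the 6-month one only if enrolment stays open throughout the extension, which section 10.2 does not say.

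**3. Chance of reaching 25.** The documents give no accrual model. Assume Poisson accrual, with pass probability P(N ≥ 25) for mean = rate × months. The rates below plan, and the halving of accrual after month 6, are illustrations.

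| Rate per month | 6 months | 12 months, constant rate | 12 months, rate halved after month 6 |
|---|---|---|---|
| 2.5 | mean 15: 1% | mean 30: 84% | mean 22.5: 33% |
| 3 | mean 18: 7% | mean 36: 98% | mean 27: 68% |
| 3.5 | mean 21: 22% | mean 42: nearly 100% | mean 31.5: 90% |
| 4.58 (planned) | mean 27.5: 71% | mean 55: nearly 100% | see below |

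At the planned rate 29% miss at 6 months. Of those, 99% would reach 25 by month 12 even if accrual halved (extra mean 13.75). If the window rolled forward, the choice of window could decide the result.

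**4. Does the text let the window roll forward?**

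- Table 2 counts patient participants.
- Section 5.3.1 defines patient participants by presentation over 6 months.
- Someone first presenting in month 9 is therefore outside the definition on the current text.
- Counting that person requires a change to section 5.3.1, and section 11.1 sends protocol revisions to all three IRBs.

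So the 12-month columns in step 3 describe a plan that has not been written.

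**5. Can the 6-month count be recovered after an extension?** Yes. Recruitment is assessed monthly, so a month-6 total will exist. Table 3 also measures DHIS2 visit capture month by month, which needs dated visits.

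**6. Follow-up row.** Assume even accrual of 100 patients over 6 months (16.7 per month). Patients with at least 3 months left number 16.7 × 3 = 50 in a 6-month pilot. In a 12-month pilot they number 100 if enrolment closes at month 6, or 16.7 × 9 = 150 if it continues. The bar stays at 75% each time. With independent patients and a true follow-up proportion of 70%:

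- n = 50: at least 38 needed, probability 22%.
- n = 150: at least 113 needed, probability 9%.

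The approximate 95% half-width at 75% is 1.96 × √(0.75 × 0.25/n): 12 points at n = 50, 8 at n = 100 and 7 at n = 150. A longer pilot makes a false pass less likely and the estimate tighter. Holding this row to the first 3 months of enrolment would discard usable patients.

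**The case for a change.** The best argument for a change is that section 10.2 is the very clause that alters the duration, and it does not say whether the inclusion period moves with it. If the window were settled in a later revision, the counts would already be known to those settling it. One sentence written now would avoid that, at almost no cost.

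Part of this stands. There is no explicit rule, the extension decision would not be blind to recruitment, and a sentence tying the enrolment rows to the original 6 months would do no harm. But it would restate what section 5.3.1 already implies, for an event that is only a possibility. Low recruitment is not named as a ground for extending. Nor does the argument carry over to the follow-up row, where an extension works against an unwarranted pass.

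Freezing the counts also has a side effect. The closing questionnaires and interviews (sections 7.3.3 and 7.3.4) would presumably move to the end of an extended pilot. The joint displays in section 9 would then set 6-month enrolment beside 12-month perceptions. That is a choice to make if an extension is proposed.

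**Conclusion.** No change is needed. The observation is accurate: the plan does not spell out how the enrolment counts are judged after an extension, and 25 in 12 months needs half the monthly rate of 25 in 6. But no rule in the plan gives a wrong answer. Read with its own definition of a patient participant, Table 2 already asks for 25 within 6 months, and analysts can report that number whether or not the pilot continues.

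Little depends on it. Section 8 reports no formal sample size calculation, the benchmarks are descriptive minimums with no test or go/no-go rule, and section 9 draws conclusions from quantitative and qualitative findings together. If an extension were proposed, the revision that authorised it would be the natural place to state the window and to report later enrolment separately.

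The pass probabilities rest on assumed Poisson accrual and an equal split of conditions between districts. Steady accrual is itself doubtful, since section 7.2 enrols existing patients, who may enter early. The conclusion does not depend on those figures; it rests on the definition in section 5.3.1 and on the month-6 count being available.

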11. ETHICAL AND OVERSIGHT CONSIDERATIONS

11.1. Plan for multiple IRBs

For this project, the study team will pursue ethics approval from the IRB of the Ministry of Health in Guatemala, as well as the IRBs at INCAP and the University of Michigan. Protocol revisions will be submitted for approval by all three IRB committees.

11.2. Study coordination with MOH

This study will be tightly coordinated with the MOH and other authorities through Technical Advisory Committee (TAC) meetings (Section 8.1.5).

11.3. Potential risks

This study involves a multilevel, multicomponent intervention to improve standard care of hypertension and diabetes at MOH primary care facilities in Guatemala. All clinical care will be provided in accordance with existing MOH protocols, by MOH health workers, in MOH-operated primary health facilities. There is no control arm. Participants include both patients receiving standard care and MOH staff who deliver or supervise standard care. The risks in participating in this study are no more than minimal because the probability and magnitude of harm or discomfort are not greater than those ordinarily encountered in routine daily life:

Psychological risks: Participants invited to participate in structured and semi-structured interviews may experience minor stress or discomfort answering certain questions. An example of a potentially uncomfortable topic for MOH participants may include interview questions relating to the quality of MOH care. An example of a potentially uncomfortable topic for patient participants might be questions about medical history, quality of life, or experiences of discrimination or abuse in the health system. We will protect against this risk by reminding participants that they can skip questions or end interview participation at any time. All research staff will complete and provide proof of completion of appropriate human subjects protection training approved by their home institution.

Risk of lost personal productivity due to the time burden of participation: Structured and semi-structured interviews are structured to last 45 minutes but may last 60 minutes or longer. Participants invited to participate in these interviews may perceive this time involvement to be a burden interfering with their other responsibilities. We will protect against this risk by offering flexible appointments for interviews, including on evenings or weekends. The study team also will be available to coordinate study visits at participants' homes or another private location requested by participants.

Loss of confidentiality risks: There is the unlikely risk of accidental disclosure of confidential data. Currently, Guatemala does not have a specific national regulation on electronic medical records or telemedicine cybersecurity.⁷¹ To protect against breach of confidentiality, all non-clinical patient data will be maintained using a unique study identification. Structured data will be securely collected using REDCap on an encrypted tablet and stored on INCAP's secure cloud server. Qualitative data from semi-structured interviews will be collected using an encrypted mobile device and stored on the University of Michigan's institutional Dropbox account. An electronic spreadsheet with the unique identification numbers will be maintained on the U-M's institutional Dropbox account, and only the PI and study coordinators will have access. Clinical patient data usually will be entered into the DHIS2 tool by MOH staff during routine clinical visits. Some MOH primary facilities may choose an asynchronous strategy in which patient data are collected using paper records and entered into DHIS2 after the routine clinical visit. These paper forms will be stored in a locked filing cabinet in a locked room at the MOH facility. The DHIS2 system will be hosted on an INCAP's secure cloud server. Password-access to DHIS2 will be restricted to relevant MOH staff, the PI, and study coordinators.

Physical risks to patient participants: A potential risk to blood glucose collection might include adverse response to a capillary blood draw, including lightheadedness, minor bleeding, or infection at the lancet site. A potential risk to patients receiving diabetes or hypertension medication treatment might include hypotension, hypoglycemia, or other adverse drug effects that have previously been described. To protect against these risks, all patients enrolled in the trial who experience these symptoms will be managed at the nearest MOH facility by MOH health workers according to national guidelines. This risk will be no higher than standard care because prescriptions will be made by MOH health workers using available medications with known, widely accepted safety profiles. The antihypertensive medications used by MOH health workers in primary health facilities include hydrochlorothiazide, enalapril, and losartan. The glucose-lowering agents used by MOH health workers include metformin and glimepiride. Insulin, which confers a higher risk of hypoglycemia, will not be used in this study because it is not available in MOH health centers or health posts.

